Grade 3	Interrupt dosing of LGX818 and MEK162 (and maintain dose level of LEE011 in patients treated in triple-combination arm) and refer patient to ophthalmologist monitoring within one week. ^g - If resolved to Grade ≤ 1 in ≤ 21 days, reduce 1 dose level ^h of LGX818 and MEK162 - If not resolved to Grade ≤ 1 in > 21 days, discontinue patient from study drug treatment and refer the patient to an ophthalmologist for monitoring. ^h
Grade 4	Discontinue patient from study drug treatment and refer the patient to an ophthalmologist for monitoring. ^g
Skin and subcutaneous tissue disorders	
Rash / hand foot skin reaction (HFSR) / photosensitivity / Toxic Epidermal Necrolysis (TEN)	
Grade 1	Maintain dose level of LGX818 and MEK162 (and LEE011 in patients treated in triple-combination arm), but consider initiating appropriate skin toxicity therapy (See Appendix 3).
Grade 2	Maintain dose level of LGX818 and MEK162 (and LEE011 in patients treated in triple-combination arm), but initiate/intensify appropriate skin toxicity therapy.
Grade 3 despite skin toxicity therapy	Interrupt dosing of LGX818 and MEK162 (and LEE011 in patients treated in triple-combination arm), until resolved to Grade ≤ 1 then: - If resolved in ≤ 7 days, ↓ 1 dose level* of LGX818 and MEK162 (and LEE011 in triple-combination arm) - If not resolved after > 7 days, discontinue patient from study drug treatment.
Grade 4 despite skin toxicity therapy	Discontinue patient from study drug treatment.

Recommended Dose Modifications for (dual) LGX818 and MEK162 or (triple) LGX818 and MEK162 and LEE011 combination study treatment	
Worst Toxicity CTCAE v4.03 Grade (unless otherwise specified)^a	Recommended Dose Modifications any time during a cycle of therapy
Respiratory, thoracic and mediastinal disorders	
ILD/Pneumonitis	Maintain dose level of LGX818; adjust dose of MEK162 (and LEE011 in patients treated in triple-combination arm) according to Grade below
Grade 1	No dose interruption or adjustment of MEK162 (or LEE011 in patients treated in triple-combination arm) is required. Initiate appropriate medical therapy and monitor as clinically indicated

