Grade 2	Interrupt dosing of MEK162 (and LEE011 in patients treated in triple-combination arm) for ≤ 21 days. -If resolved to Grade ≤ 1 in ≤ 21 days, reduce 1 dose level ^h of MEK162 (and LEE011 in patients treated in triple-combination arm), performing an individualized benefit-risk assessment -If not resolved to Grade ≤ 1 in ≤ 21 days, then discontinue patient from study drug treatment. If Grade 2 recurs, discontinue patient from study drug treatment
Grade 3/4	Discontinue patient from study drug treatment
General disorders and administration site conditions	
Fatigue	
Grades 1 or 2	Maintain dose level of LGX818 and MEK162 (and LEE011 in patients treated in triple-combination arm)
Grade 3	Interrupt dosing of LGX818 and MEK162 (and LEE011 in patients treated in triple-combination arm) until resolved to Grade ≤ 1, then: - If resolved in ≤ 7 days, maintain dose level of LGX818 and MEK162 (and LEE011 in triple-combination arm) - If not resolved after > 7 days, then ↓ 1 dose level* of LGX818 and MEK162 (and LEE011 in patients treated in triple-combination arm)
Edema	
Grades 1 or 2	Maintain dose level of LGX818 and MEK162 (and LEE011 in patients treated in triple-combination arm)

Recommended Dose Modifications for (dual) LGX818 and MEK162 or (triple) LGX818 and MEK162 and LEE011 combination study treatment	
Worst Toxicity CTCAE v4.03 Grade (unless otherwise specified)^a	Recommended Dose Modifications any time during a cycle of therapy
Grade 3	Interrupt dosing of LGX818 and MEK162 (and LEE011 in patients treated in triple-combination arm) until resolved to Grade ≤ 1, then: - If resolved in ≤ 14 days, then ↓ 1 dose level* of MEK162 and maintain dose of LGX818 (and LEE011 in patients treated in triple-combination arm) - If not resolved after > 14 days, then discontinue patient from study drug treatment.
Other adverse events	
Grades 1 or 2	Maintain dose level of LGX818 and MEK162 (and LEE011 in patients treated in triple-combination arm)
Grade 3	Interrupt dosing of LGX818 and MEK162 (and LEE011 in patients treated in triple-combination arm) until resolved to Grade ≤ 1, then ↓ 1 dose level* of LGX818 and MEK162 (and LEE011 in triple-combination arm)
Grade 4	Discontinue patient from study drug treatment.

^a All dose modifications should be based on the worst preceding toxicity.

^b Not CTCAE grading

^c Dose reduction below 50 mg QD for LGX818, and below 15 mg BID for MEK162 is not allowed.

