- Doxycycline or minocycline are not recommended due to phototoxicity and should be replaced with oxytetracycline or lymecycline. However, if doxycycline or minocycline are used, precaution measurements should be taken (i.e., avoid direct exposure on sun, use of sunglasses, sunscreen, ect.). The recommendation is: topical clindamycin (1%) plus either

hydrocortisone (2.5% cream) or pimecrolimus (1% cream) plus oxytetracycline (500 mg twice daily) or lymecycline (408 mg QD).

Severe Rash (CTCAE Grade 3-4)

CTCAE Grade 3

- The dose of LGX818 and MEK162 or LGX818 and MEK162 and LEE011 should be omitted until resolved to CTCAE Grade ≤ 1 , in line with protocol recommendations, and the rash should be closely monitored for any change in severity.
- In addition to the interventions recommended for moderate rash, prednisolone may be given (with caution due to risk of hyperglycemia) as a reducing dose regimen (25 mg for 7 days, subsequently decreasing the dose by 5 mg/day every day to 0).
- If skin toxicity CTCAE Grade 3 is not resolved within 7 days, discontinue patient from study drug treatment.

CTCAE Grade 4

- If skin toxicity CTCAE Grade 4 occurs the dose of LGX818 and MEK162 or LGX818 and MEK162 and LEE011 should be omitted and patients discontinued from study drug treatment.

Table 14-7 Treatment of skin toxicity

Mild Rash (Grade 1) Dry Skin Nail changes Pruritus Desquamation Acneiform	Topical hydrocortisone 1% or 2.5% and/or Clindamycin 1% gel
Moderate Rash (Grade 2) Dry Skin Nail changes Pruritus Desquamation Acneiform	Topical clindamycin (1%) plus either hydrocortisone (2.5% cream) or pimecrolimus (1% cream) plus oxytetracycline (500 mg twice daily) or lymecycline (408 mg QD).
Severe Rash (Grade 3-4) Dry Skin Nail changes Pruritus Desquamation Acneiform	Hydrocortisone 2.5% cream or Clindamycin 1% gel or Pimecrolimus 1% cream plus oxytetracycline (500 mg twice daily) or lymecycline (408 mg QD) plus prednisolone (with caution due to risk of hyperglycemia) (25 mg for 7 days, decreasing the dose by 5 mg/day every day).
Adapted from Thatcher 2009 .	

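### Table 6-4 gives instructions that do not agree: LGX818 in ILD/pneumonitis, Grade 3-4 skin toxicity (including TEN) against Appendix 3, and, less seriously, Grade 3 fatigue.

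*Protocol*

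**What the plan says.** All three items are in the current text of Protocol Section 6.3.2, Table 6-4, whose action column is headed "Recommended Dose Modifications any time during a cycle of therapy".

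- **ILD/pneumonitis.** The block opens with "Maintain dose level of LGX818; adjust dose of MEK162 (and LEE011 in patients treated in triple-combination arm) according to Grade below". For Grade 2 the row holds MEK162 (and LEE011) for up to 21 days and lowers their dose if the event resolves. Otherwise: "If not resolved to Grade ≤ 1 in ≤ 21 days, then discontinue patient from study drug treatment". It adds: "If Grade 2 recurs, discontinue patient from study drug treatment". The Grade 3/4 row also discontinues the patient from study drug treatment.
- **Rash / HFSR / photosensitivity / TEN.** TEN shares one block with the other skin events. The Grade 4 row is labelled "Grade 4 despite skin toxicity therapy", and the Grade 3 row carries the same qualifier. Appendix 3 (Section 14.3.1) has no such qualifier. At Grade 3 it omits the study drugs until recovery to Grade 1 or better. For Grade 4 it says "If skin toxicity CTCAE Grade 4 occurs the dose of LGX818 and MEK162 or LGX818 and MEK162 and LEE011 should be omitted" and that the patient is discontinued.
- **Fatigue, Grade 3.** Dosing of all study drugs is held until resolution to Grade 1 or better, followed by two bullets. The first keeps the dose if the event resolved within 7 days. The second reads "If not resolved after > 7 days, then ↓ 1 dose level* of LGX818 and MEK162", with LEE011 added for the triple combination.

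**The concern.** A site applying Table 6-4 needs one instruction per event and grade. For ILD, the heading and the later grade rows cannot both be followed: one keeps LGX818 at its dose, the other ends study drug treatment. For severe skin toxicity, what a site does before skin therapy has been tried depends on whether it reads the table or the appendix. For fatigue, the second bullet does not fit the sentence that introduces it.

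ILD and TEN can be life-threatening, so the first two matter for patient safety. There is also a follow-on effect for ILD. Whether LGX818 continues decides whether the patient is off treatment. That fixes the end-of-treatment visit and study completion (Section 7.1.4), the minimum 30-day adverse-event collection after the last administration (Section 8.1.1) and the on-treatment safety period (Section 10.5.2). Section 12 allows no authorized deviations, so a site that cannot satisfy both instructions has no approved way out.

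**Working it through.** No design figure (error rate, power, response rate or sample size) enters this point, so there is nothing to recompute. The check is a comparison of texts.

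**ILD/pneumonitis.** The glossary defines study treatment as the drugs tested in combination, and study treatment discontinuation as the point at which the patient permanently stops taking it. On that definition, discontinuing the patient from study drug treatment includes LGX818. Heading against rows:

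1. Grade 1: heading maintains LGX818; row requires no change to MEK162 or LEE011. They agree.
2. Grade 2, first 21 days: heading maintains LGX818; row holds MEK162 (and LEE011). They agree.
3. Grade 2, resolved within 21 days: heading maintains LGX818; row lowers MEK162 (and LEE011). They agree.
4. Grade 2, unresolved at 21 days: heading maintains LGX818; row says "discontinue patient from study drug treatment". They conflict.
5. Grade 2, recurrent: same conflict.
6. Grade 3/4: same conflict.

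So three of the six situations agree and three do not. The heading states no grade limit, time limit or exception, and nothing says whether heading or row prevails. Two features keep both readings alive. The Amendment 10 rationale describes the ILD entry as arising from MEK162 and LEE011, which fits leaving LGX818 alone. The hepatic rows speak of discontinuing from all study drug treatment, so a reader could take the ILD phrase, which lacks the word all, as narrower.

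**Skin, including TEN.** Four situations:

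1. Grade 3 despite skin therapy: Table 6-4 interrupts; Appendix 3 omits the drugs. They agree.
2. Grade 3, therapy not yet tried: the Table 6-4 skin block has no row; Appendix 3 omits the drugs.
3. Grade 4 despite skin therapy: Table 6-4 discontinues; Appendix 3 omits and discontinues. They agree.
4. Grade 4, therapy not yet tried: the Table 6-4 skin block has no row; Appendix 3 omits and discontinues.

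Table 6-3 (Section 6.2.5) is a third text. It counts Grade 3 rash, HFSR or photosensitivity as a DLT only beyond 7 days despite treatment, but Grade 4 without condition, and Section 6.2.5 interrupts the combination on a DLT. The DLT window is the first 28 days, so Table 6-3 does not itself govern patients on long-term treatment; it shows that the condition at Grade 4 is not applied consistently. Neither Table 6-3 nor the Appendix 3 algorithm names TEN, although Appendix 3 uses the general term skin toxicity.

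**Fatigue, Grade 3.** The lead-in makes both bullets follow resolution. The second bullet's own condition is that the event has not resolved. Comparable hold-then-reduce rows describe an event that did resolve, only late: Grade 3 neutropenia, thrombocytopenia and amylase/lipase (resolved in more than 7 days) and Grade 2 bilirubin (resolved in more than 21 days). The fatigue bullet departs from that pattern.

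**The case against.** The best defence on ILD is that specific rows override a general heading. Table 6-4 elsewhere maintains LGX818 during a MEK162 hold and later discontinues the patient, as in the CPK rows; the LVEF row also pairs maintaining LGX818 with discontinuation. Where one drug alone is meant, the table names it. On this view the heading covers dose adjustment and the rows cover discontinuation. That is a reasonable reading, but the parallels are not exact: in the CPK and LVEF rows, maintaining LGX818 is tied to a hold or a recovery with a stated end, whereas the ILD heading is unlimited.

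On skin, a reader might infer that the table and Appendix 3 give opposite orders at Grade 4. The documents do not support that. No Table 6-4 row says to continue dosing at Grade 3 or 4 before therapy; the block is silent. Its Grade 1 row points to Appendix 3, and the generic Grade 4 row for other adverse events also discontinues. At Grade 3, Appendix 3 says its action is in line with the protocol, which softens the mismatch there. What stands is a conditional trigger in one place and an unconditional one in another, clearest at Grade 4.

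On fatigue, the lead-in can be taken to govern both bullets, which makes the second a wording slip. It would go too far to say that the protocol orders a restart with fatigue unresolved.

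It is also fair to say that the table is headed as recommendations, that Section 6.3.1 says doses may be adjusted, that enrollment is closed and that few such events are likely.

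**Conclusion.** The inconsistencies are real and should be corrected. The ILD heading conflicts with its own rows in three situations, with no rule of precedence. The skin/TEN rows do not match Appendix 3 or, at Grade 4, Table 6-3. The fatigue bullet is minor.

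The size is limited. At Amendment 10 there were 10 patients on treatment (5 dual and 5 triple). That is the number who could be exposed to the ambiguity, not the number expected to be affected; it matters only if one of them has the event in question. No endpoint, decision rule or efficacy conclusion changes.

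Two further inferences are not supported. A reader might conclude that exposure and adverse-event tables in the final report will differ materially by site; with 10 patients and few likely events, any effect would be small, and the documents give no basis for estimating it. A reader might also attribute all three problems to Amendment 10. Its summary shows only that the ILD and TEN entries were added, not the skin-therapy qualifier or the fatigue bullet.

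The ILD conclusion assumes that the glossary meaning of study treatment applies to the phrase used in the ILD rows.

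**What to change.** The sponsor must reconcile:

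- the ILD/pneumonitis heading with its rows for unresolved Grade 2, recurrent Grade 2 and Grade 3/4, so that the status of LGX818 is explicit in each;
- the Grade 3 and Grade 4 skin/TEN rows of Table 6-4 with Appendix 3 (Section 14.3.1) and Table 6-3, so that the trigger is the same wherever it is stated, and it is clear whether the Appendix 3 algorithm covers TEN;
- the second bullet of the Grade 3 fatigue row with its lead-in sentence.

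Each should end with a single instruction. Which clinical rule applies is for the sponsor to decide. The cost is wording in three blocks of Table 6-4 and, depending on the sponsor's choice, in Appendix 3 or Table 6-3. No patients, visits or procedures are added.

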Recommended Dose Modifications any time during a cycle of therapy

Investigations (Hepatic^{})**

Bilirubin: total bilirubin without ALT/AST increase above baseline value (confirmed 48-72hr later)^c

Grade 1 (> ULN – 1.5 x ULN)	Maintain dose level of LGX818 and MEK162 (and LEE011 in patients treated in triple-combination arm) with LFTs monitored bi-weekly.
Grade 2 (> 1.5 – 3.0 x ULN)	Interrupt dosing of LGX818 and MEK162 (and LEE011 in patients treated in triple-combination arm) until resolved to Grade ≤ 1, then: - If resolved in ≤ 21 days, then maintain dose level of LGX818 and MEK162 (and LEE011 in patients treated in triple-combination arm) - If resolved in > 21 days, then ↓ 1 dose level* of LGX818 and MEK162 (and LEE011 in patients treated in triple-combination arm) - If not resolved within 28 days, or if toxicity recurs, discontinue patient from all study drug treatment. Repeat liver enzyme and bilirubin tests twice weekly for 2 weeks after dose resumption.
Grade 3 (> 3.0 x ULN)	Interrupt dosing of LGX818 and MEK162 (and LEE011 in patients treated in triple-combination arm) until resolved to Grade ≤ 1, then ↓ 1 dose level - Repeat liver enzyme and bilirubin tests twice weekly for 2 weeks after dose resumption - If not resolved within 28 days, or if toxicity recurs, discontinue patient from all study drug treatment.
Grade 4 (> 10.0 x ULN)	Discontinue patient from study treatment.

Note: If Grade 3 or 4 hyperbilirubinemia is due to the indirect (non-conjugated) component only, and hemolysis as the etiology has been ruled out as per institutional guidelines (e.g., review of peripheral blood smear and haptoglobin determination), then ↓ 1 dose level* and continue treatment at the discretion of the investigator.

AST or ALT without bilirubin elevation > 2 ULN (confirmed 48-72hr later)^c

Grade 1	Maintain dose level of LGX818 and MEK162 (and LEE011 in patients treated in triple-combination arm) and monitor LFTs biweekly.
---------	--

Recommended Dose Modifications for (dual) LGX818 and MEK162 or (triple) LGX818 and MEK162 and LEE011 combination study treatment

Worst Toxicity CTCAE v4.03 Grade (unless otherwise specified)^a

Recommended Dose Modifications any time during a cycle of therapy

AST or ALT without bilirubin elevation > 2 ULN (confirmed 48-72hr later)^c (continued)

Grade 2

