Interrupt dosing of LGX818 and MEK162 (and LEE011 in patients treated in triple-combination arm) until resolved to Grade ≤ 1 (or Grade ≤ 2 in case of liver metastasis), then:
 - If resolved in ≤ 21 days, maintain dose level of LGX818 and MEK162 (and LEE011 for triple-combination arm).
 - If resolved in > 21 days, then ↓ 1 dose level* of LGX818 and MEK162 (and LEE011 for triple-combination arm).
 - If not resolved within 28 days, discontinue patient from all study drug treatment.
Repeat liver enzyme and bilirubin tests twice weekly for 2 weeks after dose resumption.

Grade 3 (> 3.0 x ULN)

Omit dose of LGX818 and MEK162 (and LEE011 in patients treated in triple-combination arm) until resolved to ≤ baseline grade, then ↓ 1 dose level of dose level of LGX818 and MEK162 (and LEE011 in patients treated in triple-combination arm). If not recovered to ≤ baseline grade within 28 days, discontinue patient from all study drug treatment.
Repeat liver enzyme and bilirubin tests twice weekly for 2 weeks after dose resumption. If toxicity recurs, discontinue patient from all study drug treatment.

Grade 4 (> 10.0 x ULN)

Discontinue patient from study drug treatment.

AST or ALT and Bilirubin^d

For patients with normal ALT and AST and total bilirubin at baseline: AST or ALT > 3.0 x ULN combined with total bilirubin > 2 x ULN without evidence of cholestasis^e

Discontinue patient from study drug treatment.

For patients with elevated AST or ALT or total bilirubin at baseline: baseline: (AST or ALT > 2 x baseline AND > 3.0 x ULN) OR (AST or ALT 8.0 x ULN) — whichever is lower — combined with (total bilirubin > 2 x baseline AND > 2.0 x ULN)

Discontinue patient from study drug treatment.

Recommended Dose Modifications for (dual) LGX818 and MEK162 or (triple) LGX818 and MEK162 and LEE011 combination study treatment

Worst Toxicity CTCAE v4.03 Grade (unless otherwise specified)^a

Recommended Dose Modifications any time during a cycle of therapy

Investigations (Metabolic)

Asymptomatic amylase and/or lipase elevation

Grade 1 (> ULN – 1.5 x ULN)	Maintain dose level of LGX818 and MEK162 (and LEE011 in patients treated in triple-combination arm) and initiate appropriate medical therapy and monitoring.

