^d All patients with ALT or AST >5.0x ULN and total bilirubin > 1.5x ULN in the absence of cholestasis must immediately be withdrawn from study treatment and every attempt should be made to carry out the **liver event follow-up assessments** as described below in [Section 6.3.3](#).
If combined elevations of AST or ALT and total bilirubin do not meet the defined thresholds, please follow the instructions for isolated elevation of total bilirubin and isolated elevation of AST/ALT, and take a conservative action based on the degree of the elevations (e.g. discontinue treatment at the situation when omit dose is needed for one parameter and discontinue treatment is required for another parameter). After all elevations resolve to the defined thresholds that allow treatment re-initiation, re-start the treatment either at the same dose or at one dose lower if meeting a criterion for dose reduction

^e “Cholestasis” defined as: ALP elevation (>2.0 x ULN and R value (ALT/ALP in x ULN) ,2.0) in patients without bone metastasis, or elevation of ALP liver function in patients with bone metastasis.

^f All values refer to the average of triplicate measurements.

^g Ophthalmic monitoring mandated for retinal event, posterior uveitis, RVO: further evaluation with specialized retinal imaging (e.g. ocular coherence tomography, angiography).

^h Except: 1) lymphopenia unless clinically significant, 2) occurrence of KA and/or cutaneous SCC, 3) alkaline phosphatase, 4) AEs not considered clinically significant like alopecia study drug-related fever, electrolyte abnormalities (including K, NA, Cl, HCO₃, Mg, Ca, PO₄).

* ↓ 1 dose level refers to: next lower previously tested dose level of LGX818 and LEE011 and the next lower dose level of MEK162 (please see [Table 6-1](#) and [Table 6-2](#)).

Recommended Dose Modifications for (dual) LGX818 and MEK162 or (triple) LGX818 and MEK162 and LEE011 combination study treatment

**Worst Toxicity CTCAE v4.03 Grade
(unless otherwise specified)^a**

Recommended Dose Modifications any time during a cycle of therapy

** Confounding factors and/or alternative causes for increased transaminases should be excluded before dose interruption/reduction. They include but are not limited to: concomitant medications, herbal preparations or dietary supplements, infection, hepato-biliary disorder or obstruction, new or progressive liver metastasis, and alcohol intake.

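### Table 6-4 gives two incompatible orders for AST/ALT >5 to 10 x ULN with bilirubin >1.5 to 2 x ULN and no cholestasis, and its Grade 2 AST/ALT recovery target for liver-metastasis patients is already met at onset

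*Protocol*

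**What the plan says.** All of this is in Protocol Section 6.3.2, Table 6-4, unless stated otherwise.

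- **Isolated AST/ALT block.** Its title is "AST or ALT without bilirubin elevation > 2 ULN (confirmed 48-72hr later"), so it includes bilirubin up to 2 x ULN. Its Grade 3 is printed as "Grade 3 (> 3.0 x ULN") and Grade 4 as above 10.0 x ULN. The Grade 3 action is "Omit dose of LGX818 and MEK162 (and LEE011 in patients treated in triple-combination arm) until resolved to ≤ baseline grade", then a one-level reduction. Treatment stops if recovery takes more than 28 days or if the toxicity recurs. Grade 4 is discontinuation.
- **Grade 2 row of that block.** Dosing is interrupted "until resolved to Grade ≤ 1 (or Grade ≤ 2 in case of liver metastasis"). The dose is kept if this takes up to 21 days and reduced if longer; treatment stops if there is no resolution within 28 days.
- **Combined AST/ALT and bilirubin rows.** Both require bilirubin above 2 x ULN, and both discontinue.
- **Bilirubin block.** It is limited to "Bilirubin: total bilirubin without ALT/AST increase above baseline value".
- **Footnote d,** attached to the heading of the combined rows: "All patients with ALT or AST >5.0x ULN and total bilirubin > 1.5x ULN in the absence of cholestasis must immediately be withdrawn". It then continues: "If combined elevations of AST or ALT and total bilirubin do not meet the defined thresholds, please follow the instructions for isolated elevation".
- **Section 5.3, criterion 7,** admits AST/ALT up to 5 x ULN when liver metastases are present.

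**The concern.** A dose-modification table should give one action for one laboratory result. Here an investigator with ALT 6 x ULN and bilirubin 1.8 x ULN can reach either permanent withdrawal or a restart at a lower dose, depending on where the reading starts. The layout makes the second route easy. The isolated block carries marker c, which is only a dose-floor note, so nothing in it points to footnote d. The timing differs too: the isolated block allows confirmation after 48 to 72 hours, while footnote d acts at once.

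The Grade 2 row raises a different problem: for liver-metastasis patients it orders an interruption whose release condition is true when the interruption begins.

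What is at stake is liver safety in patients still on treatment. Amendment 8 was prompted partly by liver-injury findings with LEE011, and Section 1.2.2.2.1 reports a fatal acute liver failure in the MEK162 study that began at 60 mg BID.

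**Working it through.** The plan states no figure to reproduce. The check applies the printed rules to the same patient and looks for disagreement.

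**Step 1. The overlap (no cholestasis; A = AST/ALT, B = bilirubin, both x ULN).**

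- Isolated Grade 3 row (omit, then restart lower): 3.0 < A ≤ 10.0 and B ≤ 2.
- Footnote d (withdraw): A > 5.0 and B > 1.5.
- Combined rows (discontinue): both need B > 2.

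Both of the first two rules apply when 5.0 < A ≤ 10.0 and 1.5 < B ≤ 2. No combined row can apply there, because B is not above 2. The bilirubin block does not decide the case either, since it requires no AST/ALT rise above baseline.

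On a grid with steps of 0.1, the overlap is A = 5.1 to 10.0 (50 values) and B = 1.6 to 2.0 (5 values): 50 x 5 = 250 cells. Spot checks at the edges:

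| A | B | Isolated block | Footnote d | Result |
|---|---|---|---|---|
| 6 | 1.5 | restart lower | not met | no conflict |
| 6 | 1.6, 1.8, 2.0 | restart lower | withdraw | conflict |
| 6 | 2.1 | not applicable | withdraw | no conflict |
| 5.0 | 1.8 | restart lower | not met | no conflict |
| 10.1 | 1.8 | discontinue | withdraw | both stop |

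**Step 2. Does footnote d's second sentence settle it?** It sends combined elevations below the defined thresholds to the isolated rows. If those thresholds are the footnote's own (>5.0 and >1.5), ALT 6 with bilirubin 1.8 meets them and the patient is withdrawn. If they are those of the combined rows the footnote hangs on (>3.0 and >2 for normal baseline), the same patient does not meet them and is sent to the restart rule. The sentence does not say which is meant.

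**Step 3. Grade 2 row.** Trigger: Grade 2. Release with liver metastasis: Grade 2 or lower. The trigger satisfies the release whatever numerical limits define Grade 2. The required pause is therefore zero, and neither the more-than-21-days reduction nor the 28-day stop can be reached.

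**Step 4. Grade 3 row, conditional on the printed >3.0 x ULN limit.** Criterion 7 admits liver-metastasis patients up to 5 x ULN, so entry at >3 to 5 x ULN would be baseline Grade 3. Any value up to 10 x ULN is then still at baseline grade. The possible rise is 10 / entry: 10 / 3.1 = 3.2-fold, 10 / 4 = 2.5-fold, 10 / 5 = 2.0-fold. The recovery target is met at onset, the required pause is zero and the 28-day stop lapses. If the intended limit were 5 x ULN or more, this step would fall away; Step 3 would not.

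**The case against.** The best reply is that footnote d plainly governs. It is the specific rule for joint elevations, it is worded as mandatory while the table is headed as recommendations, and read in order its first sentence catches the patient before the second can send anyone to the isolated rows. The rival reading would leave the first sentence with no effect in the disputed zone. This is the natural reading, and probably the intended one. But the table states no precedence, and an investigator who starts at the isolated block meets no reference to footnote d. The footnote's advice to act conservatively does not help: it applies only when the thresholds are not met, and its example needs one parameter to require discontinuation, which neither isolated row does here.

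On Grade 2, it can be said that the protocol deliberately tolerates raised enzymes with liver metastasis and that twice-weekly tests follow resumption. That is a fair reason to want no interruption; it is not what the row says. Footnote c of the DLT table (Table 6-3) uses the same allowance coherently, because there it applies to events of Grade 3 or higher.

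On Grade 3, the objection largely succeeds. The printed AST/ALT limits for Grades 3 and 4 equal the bilirubin limits and may be a copying slip. A reader might infer that the limits are wrong, or that the Grade 3 recovery rule is broken outright. The protocol supports neither: it does not reproduce the CTCAE limits, and the recovery problem exists only if >3.0 x ULN is intended. Nor would it leave the pause without an end; it would make the required pause zero.

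**Conclusion.** Two points stand. First, for AST/ALT >5 to 10 x ULN (printed limits) with bilirubin >1.5 to 2 x ULN and no cholestasis, Table 6-4 gives both withdrawal and restart at a lower dose, without stated precedence. Outside that region the two rules do not collide; with cholestasis footnote d does not apply. Second, the Grade 2 AST/ALT row defeats itself for liver-metastasis patients, independently of any grade limit. The Grade 3 recovery target is a secondary matter, conditional on the printed limit and on entry at >3 to 5 x ULN.

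Severity is minor. Enrollment is closed (Section 14.10.1), and 10 patients were on treatment at Amendment 10, 5 of them on the triple combination. The protocol does not show whether any has liver metastases with raised entry values. Other safeguards remain: repeat liver tests, the Grade 3 dose reduction, stopping on Grade 3 recurrence, and stopping above 10 x ULN.

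A reader might also infer that trial results are compromised. They are not: ORR and DCR rest on tumor assessments, and DLTs have their own criteria in Table 6-3. At most, descriptive summaries of dose changes could reflect inconsistent handling.

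**What to change.** In Table 6-4:

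1. State that footnote d's rule (>5.0 x ULN with bilirubin >1.5 x ULN, no cholestasis) overrides the isolated AST/ALT block, keep its bilirubin threshold, and add marker d to that block.
2. Define the thresholds in footnote d's second sentence as those of footnote d and of the combined rows.
3. In the Grade 2 AST/ALT row, give liver-metastasis patients either no interruption or a recovery target that a Grade 2 event does not already meet.
4. Verify the printed Grade 3 and 4 AST/ALT limits against CTCAE v4.03. If >3.0 x ULN stands, express the Grade 3 recovery target relative to the patient's baseline value, as the second combined row does for its trigger ("AST or ALT > 2 x baseline AND > 3.0 x ULN").

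The cost is a few clarifying sentences, by amendment or site letter. No analysis changes.
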